12.10.2 Final Analysis

The data collected at the 3 month and 6 month follow up visits will be analyzed at the end of the trial after the database lock. As limited immunogenicity and safety data are collected at these time points, a CSR addendum may be written in place of a full CSR.

13 Ethical Aspects

13.1 Ethical and Legal Regulations

The PI is to ensure that this clinical trial is conducted in complete accordance with the provisions of the 2013 version of the Declaration of Helsinki, national laws, and other guidelines for the conduct of clinical trials, such as the ICH Good Clinical Practice (GCP), to guarantee the greatest possible subject protection.

13.2 Approval by IEC/IRB

The clinical trial protocol must be reviewed by the competent IEC/IRB according to the national laws of the respective CTS before the CTS enrolls its first subject in the trial.

If one of the investigators is a member of one of these committees, he/she may not vote on any aspect of the review of this protocol.

The Sponsor will assure that the IEC/IRB is informed of any amendment to the protocol and any unanticipated problems involving risks to human subjects included in the trial. Such information will be provided to the IEC/IRB at intervals appropriate to the degree of subject risk involved, but not less than once a year. Copies of all correspondence between the investigator and the IEC/IRB must be forwarded immediately to the Sponsor. If IEC/IRB approval of the trial is withdrawn, the Sponsor must be contacted immediately by facsimile, e-mail or telephone.

Clinical Trial Protocol

ABNCoV2-03

Edition 8.0

13.3 Data and Safety Monitoring

13.3.1 Data Monitoring Committee

The DMC is an independent board that oversees the safety of subjects participating in the trial. The members of the DMC are independent experts with experience in infectious diseases. The primary responsibility of the DMC is to review and evaluate the accumulated trial safety data and make recommendations whether to continue the trial to its planned conclusion.

If an event occurs which fulfills the trial halting rules (see Section 13.3.2 for further details), the DMC will review the event in a timely manner and agree whether to recommend halting or terminating the trial participation of the affected subject(s) and/or the trial as a whole. If the trial as a whole or participation of specific subjects is halted, the DMC also will decide if and when to recommend resuming the trial or subject participation in it.

A separate charter will describe in detail the relevant operational procedures, communication pathways, roles and responsibilities of the DMC.

13.3.2 Stopping Rules

The events or criteria listed below would trigger a DMC review to determine whether a temporary halting or termination for the trial as a whole is warranted:

- A serious AESI or other SAE with an at least reasonable possibility of a causal relationship to the administration of trial vaccine
- An unexpected Grade 3 or higher adverse event (e.g., a systemic reaction or lab toxicity) with at least a reasonable possibility of a causal relationship to the administration of trial vaccine
- Any case of myocarditis or pericarditis in temporal association to the administration of trial vaccine

The Medical Monitor or safety physician will review cases of Grade 3 or higher adverse events at least weekly. Any issues identified during this review can be brought to the DMC for review.

In general, any member of the DMC, the PI, and/or the BN Medical Monitor or safety physician may request a DMC review based on any observation. The DMC Chair may convene an ad-hoc meeting to review events and make recommendations with respect to the study whether or not the study stopping rules are met.

If an event fulfilling the DMC review criteria reaches the investigator's attention, the investigator has the responsibility to alert the Clinical Safety and Pharmacovigilance (CSPV) Department at email within 24 hours and provide comprehensive

Bavarian Nordic

ABNCoV2		Clinical Trial Protocol
ABNCoV2-03	Edition 8.0	

documentation of the event. A DMC meeting should be convened within 48 hours after the sponsor receives the relevant safety information.

13.4 Confidentiality and Data Protection

The PI of the respective CTS is obliged to make sure that all documents provided to third parties (e.g., in the course of a marketing authorization procedure) contain no personally identifying information.

Only a subject and site number may identify subjects. Their name or clinic and subject's medical record number may not be used. The PI keeps a separate confidential subject log for trial recruitment that allows subject numbers to be matched with names and addresses of subjects at any time. Documents not meant to be passed on to third parties must be stored securely by the PI.

Information collected during the trial may be made available to persons directly involved in this trial (PI and his staff members, monitors, statisticians), to persons authorized by the Sponsor, or to authorities. The Sponsor of the trial will only receive pseudonymized data for analysis.

14 Informed Consent

The ICF and process must comply with ICH GCP guidelines, as well as specific national regulations and/or local laws in the countries where the trial is conducted and must be approved by the appropriate IEC/IRB.

The ICF will document the trial-specific information that the investigator or his/her designee (designee must be listed on the Delegation of Authority log) provides to the subject and the subject's agreement to participate. The investigator, or designee, must explain in terms understandable to the subject the purpose and nature of the trial, trial procedures, anticipated benefits, potential risks, possible adverse effects, and any discomfort that participation in the trial may entail.

Subjects must be informed unequivocally that they may refuse participation in the trial, that they may withdraw from the trial at any time and for whatever reason, and that withdrawal of consent will not affect their subsequent medical treatment or relationship with the treating physician.

Subjects also consent to authorize the monitor, quality assurance personnel, and regulatory authorities to inspect source documents for data verification and quality assurance purposes. Such verifications will always be conducted in compliance with regulations and the terms of the informed consent and under the ethical supervision of the investigator. All aspects of the confidentiality of the subject's data will be guaranteed.

This ICF process must be documented in the subject's source record. Each subject must provide a signed and dated informed consent before any trial-related (nonstandard of care) activities are performed (such as baseline testing and data collection). The initial and any amended signed and

Bavarian Nordic

ABNCoV2		Clinical Trial Protocol
ABNCoV2-03	Edition 8.0	

dated consent forms must remain in each subject's trial file at the CTS and be available for verification by trial monitor, Sponsor/CRO auditor or competent regulatory authorities at any time. A copy of each signed consent form must be given to the subject at the time that it is signed by the subject.

15 Electronic Case Report Forms and Retention of Records

15.1 Electronic Case Report Forms

Electronic case report forms will be used to collect the clinical trial data.

All eCRFs are to be filled out completely by authorized CTS personnel. It is the investigator's responsibility to ensure that all subject data entered in the eCRF (including discontinuations or changes in trial vaccine or other medications) are accurate, complete and supported by the subject's medical records. The investigator attests to this by providing electronic signature within the electronic data capture (EDC) system.

All effort will be made by trial personnel and the PI to enter the eCRFs within the contractually agreed-upon time frame for subject visits/contacts. For any subject leaving the trial, any remaining eCRF and open queries should be completed at the time of the final visit or shortly thereafter. For subjects not fulfilling the eligibility criteria, the minimum information documented in the eCRF is the ICF information, demographics, and reason for screen failure.

The eCRFs exist within an EDC system with controlled access managed by BN or its authorized representative for this trial. Trial staff will be appropriately trained in the use of eCRFs and application of electronic signatures before the start of the trial and before being given access to the EDC system. Original data and any changes of data will be recorded using the EDC system, with all changes tracked by the system and recorded in an electronic audit trail. After database lock, the investigator will receive a copy of the subject data (e.g., paper, CD-ROM or other appropriate media) for archiving at the CTS.

15.2 Retention of Records

The investigator/trial staff must maintain adequate and accurate records to enable the conduct of the trial to be fully documented and the trial data to be subsequently verified. All essential documents, as listed in ICH GCP guidelines, will be retained by the investigator for at least 2 years after the date the last marketing application is approved for the drug in the indication being investigated and until there are no pending or contemplated marketing applications; or, if no application is to be filed or if the application is not approved for such indication, until 2 years after formal discontinuation of clinical development of the drug.
ABNCoV2		Clinical Trial Protocol
ABNCoV2-03	Edition 8.0	

The investigator must notify and obtain written approval from BN before destroying any clinical trial documents or images (e.g., scan, radiograph, ECG tracing). The Sponsor will inform the investigator of the date that the trial records may be destroyed or returned to BN.

Should an investigator wish to assign trial records to another party, advance written notice must be given to the Sponsor. Bavarian Nordic must also be notified in advance and provide express written approval of any change in the maintenance of clinical trial documents, should the investigator choose to move trial records to another location.

If the investigator cannot guarantee the aforementioned archiving requirements at the CTS for all such documents, special arrangements must be made between the investigator and BN to store these documents in secure sealed containers away from the CTS. These documents must be able to be returned in their secure sealed containers to the CTS for auditing purposes.

16 Monitoring of the Trial

16.1 Monitoring Plan

A CRO (contact information to be found in the "Responsibilities" section in the beginning of this protocol) will be contracted to perform monitoring services according to ICH GCP. Monitoring will be conducted according to the monitoring plan, which must be approved by BN. The monitoring plan will outline the monitoring strategy (including rationale) and will specify in detail the items for source data verification and other tasks, to be performed by the CRA.

Monitoring will be conducted through onsite visits with the investigator and site staff, remote monitoring, as well as any appropriate communications by mail, fax, email, or telephone. The purpose of monitoring is to ensure that the trial is conducted in compliance with the protocol, SOPs, and other written instructions and regulatory guidelines, and to ensure the quality and integrity of the data.

To assure the accuracy of data collected in the eCRFs, it is mandatory that the monitor have direct access to all original source documents, including all electronic medical records at reasonable times and upon reasonable notice. During the review of source documents, every effort will be made to maintain the privacy and confidentiality of all subjects during this clinical trial.

The site needs to maintain records to identify the nature and location of all source documents as well as essential documents.

ABNCoV2		Clinical Trial Protocol
ABNCoV2-03	Edition 8.0	

16.2 Protocol Deviations

A protocol deviation is any noncompliance with the clinical trial protocol. The noncompliance may be either on the part of the participant, the investigator, or the trial site staff. As a result of deviations, corrective actions are to be developed by the site and implemented promptly.

The PI or designee will be responsible for identifying and recording all deviations that are defined as isolated occurrences involving a procedure that did not follow the protocol or a protocol-specific procedure. All deviations from the protocol and actions taken will be recorded in the source data and placed in the trial-specific regulatory file. Protocol deviations must be sent to the local IEC/IRB per their guidelines. The site PI/trial staff is responsible for knowing and adhering to their IEC/IRB requirements. Further details about the handling of protocol deviations will be included in a trial-specific procedure.

17 Audits and Inspections

Site audits may be carried out by the BN quality assurance department or designee at any time during or after completion of this trial. All documents pertinent to the trial must be made available to the designated auditor. Subject privacy must, however, be respected. The investigator and clinical staff are to be present and available for consultation during routinely scheduled site audit visits conducted by the Sponsor or designee.

In addition, representatives from local, state, or federal regulatory authorities may choose to inspect a trial site at any time before, during, or after completion of the clinical trial. The investigator should immediately notify the Sponsor if they have been contacted by a regulatory agency concerning an upcoming inspection. In the event of such an inspection, BN will be available to assist in the preparation. All pertinent trial data should be made available as requested by the Regulatory Authority for verification, audit, or inspection purposes.

18 Responsibility of the Investigator

The investigator should be qualified by education, training, and experience to assume responsibility for the proper conduct of the trial, should meet all the qualifications specified by the applicable regulatory requirement(s), and should provide evidence of such qualifications through up-to-date curriculum vitae or other relevant documentation requested by the Sponsor, the IRB/IEC, or the regulatory authority(ies).

The PI agrees to carry out the trial in accordance with the guidelines and procedures outlined in this clinical trial protocol. The PI especially consents to strictly adhere to the ethical aspects of this protocol (see Section 13).

Changes to the protocol require written "Amendments to the protocol" issued by the Sponsor and written approval by the IEC/IRB and the PI. Changes are allowed only if the trial value is not

ABNCoV2		Clinical Trial Protocol
ABNCoV2-03	Edition 8.0	

reduced and if they are ethically justifiable. If required by the IEC/IRB, subjects will be informed of protocol changes and reconsented regarding changes that could affect subjects' willingness to continue participation in the trial.

It is within the responsibility of the investigator to ensure that the eCRF is completed in a timely manner after each subject visit and that all subject data entered in the eCRF are accurate, complete, and supported by the subject's medical records. The investigator attests to this by providing electronic signature within the electronic data capture (EDC) system.

At the conclusion of the trial, the investigator will return all partially used, unused and empty drug containers as directed by BN, or the drug containers will be destroyed at the CTS according to local legal requirements.

The investigator may ask to terminate participation in the trial due to administrative or other reasons. If this should be the case, appropriate measures that safeguard the interests of the participating subjects must be taken after verification and consultation with the PI.

The investigator will maintain appropriate medical and research records for this trial, in compliance with the ICH E6 Guideline for GCP and regulatory and institutional requirements for the protection of confidentiality of subjects. He/she will permit authorized representatives of the Sponsor and regulatory authorities to review (and, when required by applicable law, to copy) clinical records for the purposes of quality reviews, audits/inspections, and evaluation of the trial safety and progress.

The PI agrees to follow the detailed publication policy included in the clinical trial agreement.

By signing this protocol, the PI confirms that he/she has read the entire clinical trial protocol, agrees to its procedures, and will comply strictly with the formulated guidelines.

ABNCoV2-03

Edition 8.0

19 References

Appendix 1: Toxicity Scale for Laboratory Values

Grade 1 or Grade 2 toxicity is only graded according to "Toxicity Grading Scale for Healthy Adult and Adolescent Volunteers Enrolled in Preventive Vaccine Clinical Trials" if the value is outside of the institutional normal range applicable for this trial.

Estimating severity grade

For abnormalities NOT found elsewhere in the Toxicity Tables use the scale below to estimate grade of severity:

- Grade 1 An AE which is easily tolerated by the subject, causing minimal discomfort and not interfering with daily activities.
- Grade 2 An AE which is sufficiently discomforting to interfere with daily activities, but does not require medical intervention (non-narcotic pain reliever or other nonprescription medication are not considered "medical intervention" for this purpose).
- Grade 3 An AE which prevents daily activities, and which requires medical intervention (non-narcotic pain reliever or other nonprescription medication are not considered "medical intervention" for this purpose).
- Grade 4 Life-threatening or disabling

Serious or life-threatening AEs

ANY clinical event deemed by the clinician to be serious or life-threatening should be considered a Grade 4 event. Clinical events considered to be serious or life-threatening include, but are not limited to: Seizures, coma, tetany, diabetic ketoacidosis, disseminated intravascular coagulation, diffuse petechiae, paralysis, acute psychosis, severe depression.

ABNCoV2		Clinical Trial Protocol
ABNCoV2-03	Edition 8.0	

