5.3 Safety Endpoints

Safety endpoints will be summarized in Part A for all subjects receiving ABNCoV2 compared to those receiving Comirnaty and in both parts for all subjects receiving ABNCoV2. The endpoints include the frequency and percentage of subjects who report the following:

- SAEs or adverse events of special interest (AESIs) assessed as related to trial vaccine during the entire trial period, which includes both the active trial phase and follow-up.
- Grade 3 or higher adverse events (AEs) assessed as related to trial vaccine in the 8-day period starting with the day of vaccination.
- SAEs, AESIs, or medically attended AEs (MAAEs), regardless of relationship, during the active trial phase.
- SAEs, AESIs, or MAAEs, regardless of relationship, during the entire trial period.
- Grade 3 or higher AEs assessed as related to trial vaccine during the active trial phase.
- Solicited local AEs in the 8-day period starting with the day of vaccination.
- Solicited general AEs in the 8-day period starting with the day of vaccination.

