11.1.3 Unsolicited AEs

Unsolicited AEs are defined as AEs which are not pre-listed on the memory aid. Adverse events (e.g., feeling of ill-health, subjective symptoms and objective signs, intercurrent diseases, accidents, etc.) observed by the investigator and/or reported by the subject must be recorded in the eCRF regardless of the assessment of causality in relationship with the IMP/MP.

After vaccination, abnormal laboratory findings assessed as being clinically significant by the investigator are to be documented as AEs. In addition, after vaccination abnormal laboratory findings fulfilling the Grade 3 or Grade 4 criteria according to the toxicity scale (Appendix 1) are to be documented as AEs in the eCRF, regardless of whether they are considered clinically relevant. For lab values fulfilling the Grade 3 or Grade 4 criteria, the decision to repeat the labs is left to the discretion of the principal investigator (PI). Toxicity grade and seriousness of an AE will be assessed separately, i.e., a Grade 3 or Grade 4 AE will not automatically be regarded as serious.

The investigator should ask the subjects at each visit if they have experienced any AEs since their last visit. All intercurrent diseases reported by the subject need to be recorded by the investigator in the appropriate section of the eCRF.

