11.7 Unsolicited AEs

All intercurrent diseases reported when the investigator actively questions the subject will be documented and all required details (e.g., start and stop date, intensity) will be assessed. Unsolicited AEs will be reported in the subject's medical record and respective section of the eCRF (for requirements for screen failures, see Section 15.1).

Unsolicited AEs will be assessed and documented from ICF signature through EAP, and if ongoing at that time, followed until resolution or until the subject's last trial visit, at the latest. SAEs, AESIs, and MAAEs will be collected throughout the entire trial, including during the FU period.

(S)AEs would only be considered as AESIs once subject has received the trial vaccination. SAEs and AESIs will be followed-up until resolution or achievement of stable clinical conditions.

Assessment of Intensity

For all unsolicited AEs not represented in the Toxicity Grading Scale for Healthy Adult and Adolescent Volunteers Enrolled in Preventive Vaccine Clinical Trials (FDA, 2007), the maximum intensity will be based on the following descriptions:

- **Grade 1** An AE which is easily tolerated by the subject, causing minimal discomfort and not interfering with daily activities.
- **Grade 2** An AE which is sufficiently discomforting to interfere with daily activities, but does not require medical intervention (non-narcotic pain reliever or other nonprescription medication are not considered "medical intervention" for this purpose).
- **Grade 3** An AE which prevents daily activities, and which requires medical intervention (non-narcotic pain reliever or other nonprescription medication are not considered "medical intervention" for this purpose).
- Grade 4 Life-threatening, or disabling.

Assessment of Causality

The relationship between the occurrence of an AE and the IMP will be assessed using the categories presented below. For expedited reporting and all other purposes, the categories "not related" and "unlikely" will represent no evidence or argument to suggest a causal relationship,

Bavarian Nordic

ABNCoV2		Clinical Trial Protocol
ABNCoV2-03	Edition 8.0	

while "possible", "probable" and "definite" will be seen to convey that there is evidence or argument to suggest a causal relationship. To ensure reporting, all AEs without a causality assessment from the investigator will preliminarily be classified as "possible".

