#### 4.5.2.6. Unsolicited Adverse Events

Unsolicited AEs will be assessed and documented from ICF signature through EAP, and if ongoing at that time followed until resolution or until the subject’s last trial visit, at the latest. SAEs, AESIs, and MAAEs will be collected through the end of the trial, including during the FU phase, and followed-up until resolution or achievement of stable clinical conditions.

Unsolicited AEs are graded based on the *Toxicity Grading Scale for Healthy Adult and Adolescent Volunteers Enrolled in Preventive Vaccine Clinical Trials*. The maximum toxicity grade over the duration of the AE will be reported in the eCRF. If a subject has multiple AEs

within the same PT, the highest toxicity grade will be used for subject-level summaries. Grading will be based on the descriptions listed in [Table 8](#).

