**Table 8: Adverse Event Grading**

Grade	Definition
Grade 1	An AE which is easily tolerated by the subject, causing minimal discomfort and not interfering with daily activities.
Grade 2	An AE which is sufficiently discomforting to interfere with daily activities, but does not require medical intervention (non-narcotic pain reliever or other nonprescription medication are not considered “medical intervention” for this purpose).
Grade 3	An AE which prevents daily activities and which requires medical intervention (non-narcotic pain reliever or other nonprescription medication are not considered “medical intervention” for this purpose)
Grade 4	Life-threatening, or disabling.

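### Appendix 1 makes any clinical event deemed serious Grade 4, while Section 11.7 and SAP Table 8 grade by intensity, and nothing says which rule governs the analysed grade

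*Protocol*

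**What the plan says.** Protocol Appendix 1 gives a four-step intensity scale for abnormalities that the toxicity tables do not list. Its top step reads "Grade 4 Life-threatening or disabling". Under a separate subheading the same page adds: "ANY clinical event deemed by the clinician to be serious or life-threatening should be considered a Grade 4 event".

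Protocol Section 11.7 uses the same four steps for unsolicited adverse events (AEs) that are not in the FDA 2007 toxicity scale. It ends at "Grade 4 Life-threatening, or disabling" and has no clause on seriousness. SAP Table 8 repeats the scale, again with Grade 4 as "Life-threatening, or disabling".

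Protocol Section 11.1.3 says "Toxicity grade and seriousness of an AE will be assessed separately". It then explains this in one direction only: a Grade 3 or 4 event is not serious merely because of its grade.

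On the source of the analysed grade, SAP Section 4.5.2.6 says "The maximum toxicity grade over the duration of the AE will be reported in the eCRF". Protocol Section 5.3 lists two endpoints built on grade: related AEs of Grade 3 or higher in the 8 days from vaccination, and "Grade 3 or higher AEs assessed as related to trial vaccine during the active trial phase".

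**The concern.** Seriousness and intensity are different scales. Section 11.1.5 makes an event serious through hospitalization, or as an otherwise important medical event, with no threat to life and no disability. Section 11.9.2 goes further for myocarditis and pericarditis. Cases in temporal association with vaccination are treated as serious and potentially related even when no other seriousness criterion is met.

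A site that follows Appendix 1 enters Grade 4 for all of these. A site that follows Section 11.7 enters the intensity. Neither document says which text prevails, and no central re-grading of unsolicited AEs is described. The Grade 3-or-higher counts could therefore mix two definitions across sites. At stake are the two related-event endpoints, the SAP tables of AEs of Grade 3 or higher, and the weekly review of such events in Section 13.3.2. The immunogenicity conclusions are not affected.

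**Working it through.** The plan gives no figure to reproduce here, so the check is a comparison of rules followed by a per-subject sensitivity.

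**Step 1: which events are graded differently.** Take a serious clinical event that is neither life-threatening nor disabling and is not in the FDA 2007 scale.

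| Intensity under 11.7 / Table 8 | Grade under Appendix 1 | Grade 3 or higher under 11.7? | Grade 3 or higher under Appendix 1? |
|---|---|---|---|
| 1 | 4 | no | yes |
| 2 | 4 | no | yes |
| 3 | 4 | yes | yes |

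Only serious events of intensity Grade 1 or 2 change the count. For intensity Grade 3 only the split between Grades 3 and 4 moves, and neither endpoint uses that split. Hence:

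subjects counted under Appendix 1 = subjects counted under 11.7 + subjects whose only qualifying event is serious with intensity Grade 1 or 2.

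For the two endpoints in Section 5.3 the event must also be related.

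**Step 2: can such an event reach the related endpoints?** Yes. A mild, temporally associated myocarditis or pericarditis case is serious and potentially related under Section 11.9.2. Section 11.7 counts a possible relationship as related. If its intensity is Grade 1 or 2, the case is outside the Grade 3-or-higher endpoints under Section 11.7 and inside them under Appendix 1.

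**Step 3: size per reclassified subject.** The documents give no number of serious events of low intensity, so only the shift per subject can be computed.

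- Part A, one cohort arm: 500 planned per cohort, randomized 1:1, gives 250. 1/250 = 0.4 percentage points.
- Part A, ABNCoV2 arm over both cohorts: 2 × 250 = 500. 1/500 = 0.2 points.
- All ABNCoV2 recipients: 3000 planned (protocol Section 12.2.2). 1/3000 = 0.03 points.

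These are planned denominators. SAP Section 2.1 reports that Part A Cohort 1 under-enrolled, so the shift per subject there is larger than 0.4 points. The 3000 matches the all-ABNCoV2 summary in protocol Section 5.3, whereas the SAP tabulates AEs by trial part.

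As an illustration only, assume 0 to 5 reclassified subjects. That gives 0 to 5/500 = 1.0 point in the Part A ABNCoV2 arm if all fall there, or 0 to 5/3000 = 0.17 points in the 3000.

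**The case against.** - **Appendix 1 is about laboratory values.** Its title says so, and Section 11.1.3 cites it only for laboratory grades. But the sentence covers any clinical event and is followed by clinical examples such as seizures, paralysis and acute psychosis. The title does not remove the conflict.
- **Serious may be meant loosely, as clinically grave.** The examples lean that way and the wording leaves it to the clinician. The protocol defines the term once, in Section 11.1.5, and Appendix 1 offers no other meaning. This lowers confidence about what sites did; it does not settle which rule applies.
- **Section 11.1.3 does not contradict Appendix 1.** A reader might infer a flat contradiction. The explanation given there says only that high grade does not imply seriousness, while Appendix 1 runs from seriousness to grade. The tension rests on the general statement that the two are assessed separately. The conflict with Section 11.7, SAP Table 8 and Appendix 1's own Grade 4 line does not depend on it.
- **Grade 4 is not reserved for life-threatening or disabling events throughout.** This is correct. Section 11.7 yields to the FDA 2007 scale, and SAP Table 9, which follows that scale, assigns Grade 4 to certain emergency-room visits or hospitalizations. The point is therefore confined to unsolicited AEs outside that scale.
- **Most serious events would be Grade 3 anyway.** This largely stands. Under Section 11.7, Grade 3 requires prevented daily activities and medical intervention, which in-patient hospitalization will ordinarily satisfy.
- **Little turns on it.** Safety analysis is descriptive, related serious AEs have their own endpoint and tables, and a related serious AE or any temporally associated myocarditis or pericarditis already triggers data monitoring committee review. This also stands, and it is why the point is minor.

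**Conclusion.** The contradiction is real and lies in the current Edition 8.0 text. For unsolicited AEs outside the FDA 2007 scale, a serious event of intensity Grade 1 or 2 has two possible grades, on opposite sides of the threshold used by two safety endpoints. The SAP analyses whichever grade the site entered.

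The effect is probably small: 0.4 percentage points per reclassified subject in a planned Part A cohort arm and 0.03 points in the planned 3000. A reader might infer that the Grade 3-or-higher tables are substantially inflated or largely duplicate the serious-event tables. The documents do not support that. They give no rate of serious events and no share of them with low intensity, and most hospitalized events would count under either rule. This is a low-priority clarification. It rests on reading serious in Appendix 1 as Section 11.1.5 defines it.

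**What to change.** - **Protocol Appendix 1:** reconcile the passages by rewording the one sentence so that it agrees with Section 11.7 and SAP Table 8 and seriousness alone does not set the grade.
- **SAP Section 4.5.2.6:** state that, for unsolicited AEs not in the FDA 2007 scale, the analysed grade is the Section 11.7 / Table 8 intensity grade. Carry over the protocol's restriction to events outside that scale, which the SAP text does not spell out.
- **Leave unchanged:** grading of events in the FDA scale, solicited AEs (SAP Tables 6 and 7), vital signs (SAP Table 9) and laboratory values. Seriousness needs no new output, because the planned serious-AE tables already report it separately.
- **Before lock:** query serious AEs in this category that are graded 4 with neither a life-threatening nor a disabling criterion. The eCRF records the seriousness criteria (SAP Section 4.5.2.1), so this is a short listing that can be run without treatment assignment.

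The cost is one protocol sentence, one SAP sentence and a small query. The change concerns a reporting definition and does not alter how subjects are managed.
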